Participants randomized to the facilitated DOT arm will attend the Mulago ISS clinic on a weekly basis to ingest 3HP medication under direct observation. DOT will be defined as a designated clinic staff member observing ingestion of each dose of 3HP. Additionally, participants randomized to facilitated DOT will receive:

1. DOT cards with instructions to present directly to the pharmacy for a pharmacy-only visit, without the need to wait in the general queue.
2. Automated SMS or interactive voice response (IVR) phone call reminders at no cost to participants the day before each appointment.
3. A fixed level of reimbursement (~\$5-8/visit) for each weekly visit, conditional on either directly observed therapy or evidence of an adverse event that would preclude further treatment.

Participants who fail to return for a scheduled appointment within 24 hours will receive an SMS or IVR phone call reminder for three consecutive days after the missed appointment.

Arm 2: Facilitated SAT

Participants randomized to the facilitated SAT arm will take their first dose of medication under direct observation and be provided with a 4-week supply of 3HP to take weekly via self-administration. Participants will be asked to return to the Mulago ISS clinic after completing their 5th dose to review adherence data with the Mulago ISS clinic pharmacy technician and receive 5 additional doses of 3HP (doses 7-11). At the scheduled refill visit (dose 6) and the end-of-treatment visit (dose 12), participants will ingest 3HP doses under direct observation. Additionally, participants will receive:

1. 99DOTS-based digital adherence technology to monitor and promote adherence.
2. Weekly check-ins via two-way SMS or IVR phone call for dosing reminders and messaging asking "Are you well?" (or other similar message, as determined in our formative research phase), to serve as an alternative to weekly visits with a health worker to inquire about potential side effects
3. A fixed level of reimbursement (~\$5-8/visit) for the refill and end-of-treatment visit, conditional on either directly observed therapy or evidence of an adverse event that would preclude further treatment.

Participants who fail to return for a scheduled appointment within 24 hours will receive an SMS or IVR phone call reminder for three consecutive days after the missed appointment.

Arm 3: Patient Choice between facilitated DOT and facilitated SAT

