- Facilitated DOT participants:** After ingesting their first dose, participants will be instructed to select a date and time to attend the Mulago ISS clinic on a weekly basis. Participants will then be given a DOT card with instructions to present directly to the pharmacy for a pharmacy-only visit, without the need to wait in the general queue on their next visit date, and every visit date thereafter. Participants will be informed that they will be reimbursed at a fixed rate for weekly visits.
- Facilitated SAT participants:** After ingesting their first dose, participants will be asked to demonstrate knowledge of the appropriate dosing of 3HP, common side effects, and how to confirm dosing by making calls using the toll-free numbers. The patient will then be given sufficient pills for four doses of rifapentine and isoniazid. Participants will be asked to return to the Mulago ISS clinic at Week 6 with remaining pills (if any). Participants will be reminded that the scheduled Week 6 visit will be reimbursed at a fixed rate.

Weekly or Monthly during 3HP treatment

The following *routine* TB preventive care activities will be performed by Mulago ISS clinic staff during all 3HP DOT or refill visits:

1. **Adherence assessment:** The pharmacy technician will record in the clinic 3HP dosing register whether patients swallowed all prescribed pills including date and time of ingestion and, for patients taking 3HP by SAT, the technician will determine the number of doses taken based on 99DOTS medication adherence reports, pill counts and the participant's self-report. In addition, the pharmacy technician will receive an automated SMS when a participant does not return for a scheduled dosing visit (all participants) or does not confirm dosing by calling the toll-free number within 24 hours of a scheduled 3HP dose (Facilitated SAT participants). The technician will be encouraged to call such participants to inquire about the reason for not taking their scheduled dose and provide additional counseling as needed. Participants will be considered to have failed to complete treatment within 16 weeks if they miss 6 or more doses during 3HP treatment.
2. **Adverse events screening:**

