3. **Active TB assessment:** The pharmacy technician will perform symptom screening using the Mulago ISS clinic intensified case finding form, and refer symptomatic patients to Mulago ISS clinicians for further evaluation. The clinician will make all decisions regarding TB testing, initiation of TB treatment, and continuation/discontinuation of 3HP.
4. **Medication administration:**

- a. **Facilitated DOT:** For all scheduled visits, medications will be prepared in advance. The pharmacy technician will address any patient questions about treatment, confirm continued interest in taking medications, provide INH and RPT tablets (as loose pills or fixed dose combination pills), with or without pyridoxine, and observe medication ingestion.
- b. **Facilitated SAT participants:** At weeks 6 and 12, participants will return to the Mulago ISS clinic. The pharmacy technician will address any patient questions about treatment, confirm continued interest in taking medications, provide INH and RPT tablets (as loose pills or fixed dose combination pills), with or without pyridoxine, and observe medication ingestion. At the week 6 visit, the technician will also provide additional doses of 3HP until the end-of-treatment visit and remind the patient about side effects.

5. **Participant reimbursement:** At each visit, the pharmacy technician will give DOT participants cash reimbursement for expenses related to transportation and food. SAT participants will be reimbursed at the same fixed level as DOT participants but only at their refill visit at week 6 and end-of-treatment visit at Week 12. A fixed level of reimbursement will be determined in our formative assessment and based off of current local transportation costs [which have doubled during the COVID pandemic] but will total approximately US\$5-8 (15,000-30,000 USh) per visit. Receipt of this reimbursement will be conditional on either directly observed therapy or evidence of an adverse event that would preclude further treatment.

The following *study-specific activities* will be performed by research staff during 3HP DOT or refill visits:

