4. **Patient Costing:** To estimate any additional patient-level and societal costs of 3HP (e.g., ancillary healthcare visits, patient and caregiver costs associated with 3HP, use of formal social support programs), the time-and-motion studies will be supplemented by a patient costing survey (N=150, or 50 participants per arm).

Post-3HP treatment

All participants will be aggressively traced and asked to return to clinic (reimbursed in the usual fashion) after completion of their final medication dose, or at 16 weeks post-treatment initiation (for participants not completing treatment).

The following *routine TB preventive care activities* will be performed by Mulago ISS clinic staff during a routine HIV/AIDS care clinic visit:

Follow-up assessment: Participants will be screened for active TB for a period of two years after 3HP treatment completion (*i.e.*, up to 28 months after enrollment) at clinic visits for routine HIV/AIDS care. TB screening will include symptom assessment using the WHO four-symptom TB screen administered at every visit. For patients with new or progressive TB symptoms a chest X-ray (**CXR**) and sputum for Xpert MTB/RIF and mycobacterial culture will be performed, as per routine WHO and NTLP recommended procedures. Sputum will be induced, if needed. All participants diagnosed with TB at any time point will have sputum submitted for culture and drug susceptibility testing on liquid media. Loss to follow-up will be defined as a participant not able to be contacted and does not return to clinic within the 12-month post treatment follow-up period. At 28 months only, all clients who have not already been diagnosed with TB at any point during follow-up and regardless of any symptoms of TB will be asked to return to the clinic and submit sputum for Xpert MTB/RIF and mycobacterial culture for those with RIF resistance detected via Xpert MTB/RIF.

The following *study-specific activities* will be performed by research staff after 3HP treatment is complete:

1. **Survey 3:** Research staff will administer a survey to document the reason for treatment discontinuation (completed therapy, adverse event/intolerance, other) and to assess satisfaction with TB preventive care received. Study staff will use patient telephone numbers and addresses to contact study participants. If returning to clinic is not possible, the survey may be conducted over the phone.

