2. **In-depth Interviews:** will be conducted with patients to identify processes and contextual factors that influenced patient's acceptance and completion of 3HP under each delivery strategy. For each of the three delivery strategies, 24 participants (72 in total) will be purposively sampled to include those who completed all 12 doses, those who only completed the doses after being reminded for 3 days after missing the originally scheduled dose and those who failed to complete the doses despite the reminders on the day before and 3 days after the missed dose or clinic appointment. The interviews will be conducted in either English or Luganda depending on the participants' preference. The interviews will be audio recorded and later transcribed in readiness for analysis. Transcripts for interviews conducted in Luganda will be translated to English.
3. **Key Informant Interviews** will be conducted with health service providers to identify clinic-level facilitators and barriers to adoption and implementation of 3HP under each delivery strategy. Participants for the key informant interviews will be purposively sampled based on their cadres (*e.g.* Doctors, Clinical officers, Pharmacists, Pharmacy technicians, Nurses, Counselors, Peer educators and administrators) and on their involvement in the delivery of 3HP. Up to 10 providers (N=10) will be selected to take part in the key informant interviews. Key informant interviews will be conducted mainly in English by trained staff, audio-recorded and professionally transcribed.

Table 2. Participant data collection and measurements.

Procedure	Day 1	Weekly (DOT) or 6-week refill visit (SAT) during 3HP treatment (Weeks 2-11) ^a	Post-3HP treatment	
			Week 12 ^a	Every 2-3 Months (Months 3-28) ^a

Baseline questionnaire - Demographic and clinical information	X			
Survey 1 - Cost (to access clinic) - Knowledge/Beliefs/Support	X			
Survey 2^b - Reasons for choice	X			
Time-and-Motion studies^c		X		
Patient costing survey^d		X		
3HP adherence assessment		X	X	
Adverse events assessment		X	X	
Active TB assessment^e		X	X	X
3HP delivery process metrics		X		
Survey 3 - Satisfaction with care			X	
In-depth interview^f			X	

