### 3.7 Analysis of secondary outcomes

Secondary outcome analysis will include:

1. **Reach outcome(s):** 1) Unadjusted comparisons across arms, and 2) simple calculation of the proportion of patients randomized who accept treatment in each arm.
2. **Effectiveness outcomes:** 1) Occurrence of AEs across arms will be assessed using Chi-square tests and logistic regression; 2) Incidence of active TB will be assessed using Kaplan-Meier curves, log-rank tests, and Cox proportional hazards methods as appropriate. Assessment for active TB occurs at 15-16 months post enrolment. Survival analyses will include:
  - o An assessment of the incidence rate of TB, comparing across arms (DOT vs. SAT vs. Choice) using Kaplan Meier, time-to-event analyses. We will estimate the difference in the Kaplan Meier and Cox proportional hazard estimators for the survivor functions, comparing the arms to get hazard ratios and 95% CIs.
  - o An assessment of the incidence rate per arm by drug compliance, which will include for each arm: a comparison of the incidence of active TB in those within the arm that complete at least 11 of the 12 doses within the allotted 16 weeks vs. the incidence of active TB in those within the arm that complete  $\leq$ 10 doses of 3HP. We will estimate the difference in the Kaplan Meier and Cox proportional hazard estimators for the survivor functions, comparing the arms to get hazard ratios and 95% CIs.

3. **Adoption outcomes:** For each process metric, we will report the monthly proportion (and 95% CI) number, or median (interquartile range (IQR)) to assess the implementation of intervention components in each arm.
4. **Implementation outcomes:** Quantitative data will be assessed using multivariable regression models to compare by study arm patient survey data including a) patient costs; b) scores on questions related to patient barriers to TB preventative care; and c) patient satisfaction. Qualitative data will be analysed using appropriate software where open coding will be applied to generate codes and themes. Thematic groupings will be developed and reviewed to identify emergent themes within each domain of the coding framework and quotes that best represent each domain. Thematic interpretation will include collaborative development of a coding framework and detailed coding of transcripts.

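### TB symptom screens during treatment differ by arm (11 in DOT, 2 in SAT), and the SAP compares TB across arms without showing or testing what this does to the result

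*SAP*

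**What the plan says.** **During treatment.** Protocol section IV (Study Procedures) states that routine "TB preventive care activities will be performed by Mulago ISS clinic staff during all 3HP DOT or refill visits". TB screening is one of these activities: "The pharmacy technician will perform symptom screening using the Mulago ISS clinic intensified case finding form". Arm 1 participants "attend the Mulago ISS clinic on a weekly basis to ingest 3HP medication under direct observation". For SAT, "At weeks 6 and 12, participants will return to the Mulago ISS clinic". Choice participants follow the schedule of the mode they pick and may switch at any time. Symptomatic patients are referred, and "The clinician will make all decisions regarding TB testing, initiation of TB treatment, and continuation/discontinuation of 3HP".

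**After treatment.** All arms move to a common scheme: "TB screening will include symptom assessment using the WHO four-symptom TB screen administered at every visit". Visits fall every 2-3 months (note to Figure 1), with chest X-ray, Xpert and culture for new or progressive symptoms. Sputum regardless of symptoms is requested once, at 28 months.

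**Event definition.** Secondary objectives 5 and 6 in protocol section III class TB as definite (positive Xpert or culture) or probable (treatment started at clinician discretion, followed by improvement).

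**Analysis.** SAP 3.7, item 2, specifies "An assessment of the incidence rate of TB, comparing across arms (DOT vs. SAT vs. Choice) using Kaplan Meier, time-to-event analyses", with hazard ratios and 95% confidence intervals. It does not say whether probable TB is included or handled separately. It contains no early/late split, no landmark and no sensitivity analysis for unequal screening. The SAP's TB objective (section 2.1) stops at 16 months.

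**The concern.** Kaplan-Meier curves, the log-rank test and Cox regression all use the date of diagnosis. If one arm is screened weekly and another about every six weeks, the same disease is dated earlier in the first arm. If some illness resolves, or some discretionary diagnoses are prompted by passing symptoms, the weekly arm also collects more events.

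TB present at entry adds to this. Exclusion criterion (a) removes people who are symptom-positive and also have elevated CRP, or who have current or planned TB treatment. Missed cases can therefore enter, and they meet their first on-treatment screen in week 2 in DOT but in week 6 in SAT.

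At stake is the reading of the trial's TB outcome. An excess of TB in DOT could reflect how often staff looked. The primary outcome is not affected.

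**Working it through.** The documents give no TB incidence, event count or power for this comparison, so there is no stated figure to reproduce.

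**1. Scheduled screens.**
- Weeks 2-12: DOT 11, SAT 2 (weeks 6 and 12). Ratio 11/2 = 5.5.
- Post-treatment visits every 2-3 months give 4-6 more by month 16 in every arm. Totals: DOT 15-17, SAT 6-8.

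**2. Wait from onset to next scheduled screen.**
- DOT: 1/2 = 0.5 week.
- SAT: intervals of 5 and 6 weeks give (5²/2 + 6²/2)/11 = 30.5/11 = 2.8 weeks.
- After treatment, all arms: half of 2-3 months, or 4.3-6.5 weeks.

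**3. Share of follow-up.** 12/69.6 weeks = 17% of 16 months; 16/69.6 = 23%.

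**4. Simulation with identical true disease in DOT and SAT, 552 per arm.** Assumptions not in the documents: incidence 0.5-2 per 100 person-years; undetected TB at entry 0-1%; per-screen sensitivity 30-70%; full attendance; post-treatment visits every 2.5 months; all TB still present at 28 months found by the sputum test.

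| DOT:SAT ratio of detected TB | Week 12 | 16 months | 28 months |
|---|---|---|---|
| Disease persists until found | 1.11-2.00 | 1.00-1.06 | 1.00 |
| Detectable for a mean of 8 weeks | 1.6-3.2 | 1.1-2.4 | 1.07-2.0 |

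At 16 months the DOT excess is 0-0.6 cases under persistence and 0.2-3.4 if disease is transient. The highest 16-month ratio in each row comes from incidence 0.5, entry TB 1% and sensitivity 30%: 7.87/7.39 = 1.06 (persistent) and 4.73/1.95 = 2.43 (transient).

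**5. Cross-check by direct arithmetic.** Assume 5% of screens positive, 1-2% of referrals ending in unconfirmed treatment, and true incidence 0.5-1.5 per 100 person-years.
- True cases: 552 × 16/12 × 0.005 to 0.015 = 3.7 to 11.0 per arm.
- On-treatment referrals: DOT 552 × 11 × 0.05 = 304; SAT 552 × 2 × 0.05 = 55.
- Unconfirmed diagnoses: DOT 3.0-6.1; SAT 0.6-1.1.
- Ratio, counting on-treatment screens only: (11.0 + 3.0)/(11.0 + 0.6) = 1.21, up to (3.7 + 6.1)/(3.7 + 1.1) = 2.04.
- Applying the same rates to the 4-6 post-treatment screens lowers the top to between (3.68 + 552 × 15 × 0.001)/(3.68 + 552 × 6 × 0.001) = 11.96/6.99 = 1.71 and (3.68 + 552 × 17 × 0.001)/(3.68 + 552 × 8 × 0.001) = 13.06/8.10 = 1.61. The low end stays near 1.2.

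**6. Starting the comparison at week 16 instead.** In the simulation no screen falls between weeks 12 and 16, so later cases are the 16-month count minus the week-12 count. Under persistent disease:
- Incidence 0.5, entry TB 1%, sensitivity 30%: DOT 7.87 - 5.86 = 2.01; SAT 7.39 - 3.04 = 4.35; ratio 0.46.
- Incidence 0.5, entry TB 0, sensitivity 70%: DOT 3.27 - 0.56 = 2.71; SAT 3.27 - 0.46 = 2.81; ratio 0.96.

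The landmark therefore gives about 0.5-1.0 with no true difference. SAT carries undetected cases past week 16, and DOT has already cleared its own.

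**7. Precision.** Events expected in two arms by 16 months: 2 × 552 × 0.005 to 0.02 × 16/12 = 7.4 to 29.4. Power for a hazard ratio of 0.5 (Schoenfeld, two-sided 0.05) is 15-47%. With so few events, two or three extra diagnoses can move the estimate.

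**The case against.** The strongest reply is that the planned analysis is nearly unbiased where it matters most. Tuberculosis that persists will be found later in SAT, and the 16-month ratio is then 1.00-1.06. This stands, and it is why the analysis from enrolment should not be replaced.

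Four further points have force:
- The SAP has a TB assessment at 15-16 months in all arms, though its content is not described, and the protocol requests sputum from every undiagnosed participant at 28 months. Both pull the arms together. The 28-month test comes after the SAP's 16-month endpoint.
- SAT participants get a weekly check-in, with calls or a home visit after a negative or missing reply, and possible referral to a clinician. This narrows the gap in contact. The follow-up uses a side-effect checklist, however, so it is not a TB screen.
- Probable TB requires later improvement, repeated weekly screens of one lingering symptom are not independent chances, and some DOT visits will be missed. Each reduces the upper figures.
- Part of the remedy exists already: definite and probable categories are defined, and TB screening at visits is an adoption metric.

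A reader might also infer that the change of instrument, work-up and interval after treatment biases the arms. The documents do not support that. The change applies to every arm, and the content of the clinic's case-finding form is not given. The change makes early and late person-time less comparable but does not itself favour an arm.

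**Conclusion.** The point holds in conditional form. Unequal screening by randomized arm is fixed by the protocol, discretionary diagnoses count as events, and SAP 3.7, item 2, has nothing that would show whether a difference between arms comes from them. If missed disease persists, mainly the timing shifts. If symptoms or discretionary diagnoses are transient, DOT could show about 1.1-2.4 times as much TB at 16 months with no true difference. These sizes rest on assumed incidence, entry TB, sensitivity and duration, none of which the documents give.

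Two stronger readings are tempting. One is that DOT will look worse. The documents do not settle which kind of disease dominates, so the inflation may be close to nil. The other is that a comparison starting at week 16 would remove the problem. Being TB-free at week 16 is itself a result of the unequal screening, and under persistent disease the landmark falsely favours DOT. Nor does week 16 after enrolment guarantee a common schedule for all, because treatment may run 16 weeks from initiation.

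This is a secondary outcome with few expected events, so the change is worthwhile but not critical.

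**What to change.** In SAP 3.7, item 2, keep the intention-to-treat comparison from enrolment as the main TB analysis and name enrolment as time zero. The SAP does not state it, and the footnote to the protocol's outcome table refers to a 28-month post-treatment period while the follow-up section counts 28 months from enrolment. Then add:

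1. TB diagnosed before and after week 16, by arm, split into definite and probable, with the number of TB screens actually done per arm.
2. A comparison restricted to definite TB.
3. A week-16 landmark comparison among randomized participants then under follow-up and TB-free, as a sensitivity analysis only. State that it conditions on being TB-free after unequal screening, that it can be biased in the opposite direction, and that it is to be read beside the main analysis.

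The cost is SAP wording and a little extra analysis on data already being collected. The restricted analyses have fewer events and less precision: the landmark drops cases from the first 23% of 16-month follow-up, and the definite-only analysis drops probable cases.

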^a 3HP treatment may last up to 16 weeks^b Patients randomized to choice arm only^c Time-and-motion studies will be performed on 40 randomly selected days (one day per week throughout the year, stratified by day of week). We anticipate that this will capture up to 250 unique participant visits per arm (750 total).^d Patient costing surveys will include 50 participants from each arm, or 150 participants total^e Only if symptomatic, except at end of follow-up.^f 24 participants/arm

Outcome Measures

Primary Outcome (Effectiveness of delivery options)

Outcome	Numerator	Denominator
Proportion accepting and completing 3HP treatment	Number who take at least 11 of 12 doses within 16 weeks of treatment initiation	Number randomized

Secondary Outcomes (Quantitative)

Outcome	Numerator	Denominator
REACH		
Treatment acceptance	Number taking at least one dose of 3HP	Number randomized
EFFECTIVENESS		
Treatment completion	Number who take at least 11 of 12 doses within 16 weeks of treatment initiation	Number taking at least one dose of 3HP

Cost-effectiveness (overall)	(Cost in Arm A – cost in Arm B) from societal perspective	(DALYs averted in Arm A – DALYs averted in Arm B) from societal perspective
Cost-effectiveness (health system)	As above, but from health system/provider perspective	As above, but from health system/provider perspective
Cost-effectiveness (patient)	As above, but from patient perspective	As above, but from patient perspective
Safety	Number for whom treatment discontinued due to adverse events or intolerance.	Number taking at least one dose of 3HP
Cumulative incidence of TB at 16 months	Number diagnosed with TB during 16-month follow-up	Risk set*
Cumulative incidence of TB at 28 months	Number diagnosed with TB during 28-month follow-up	Risk set*
ADOPTION		
All Participants		
Visit Cost Reimbursement	Number of visits for which reimbursement provided on same day	Total number of DOT/refill visits
Time to complete clinic visit	Mean and median number of minutes for each DOT/refill visit	--
SMS or IVR phone call reminders delivered	Number of SMS or IVR phone call dosing or clinic visit reminders delivered	Total number of SMS reminders scheduled to be sent
SMS or IVR phone call reminders following missed appointments	Number of SMS or IVR phone call dosing or clinic missed appointment reminders delivered	Number of participant weeks with 3HP missed appointments
Screening for active TB	Number screened for active TB during DOT visits	Total number of DOT visits

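### The within-arm TB comparison by doses taken (SAP 3.7) has no stated time origin or landmark; on one reading of the clock it can favour completers when completion has no effect

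*SAP*

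**What the plan says.** SAP 3.7, item 2, plans two survival analyses of active TB. The first compares the randomised arms. The second, at issue here, works within each arm. It sets the "incidence of active TB in those within the arm that complete at least 11 of the 12 doses within the allotted 16 weeks" against that in participants taking 10 doses or fewer, using Kaplan-Meier and Cox. Its last sentence still speaks of comparing the arms, although the contrast just described is between dose groups.

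The bullet names no time origin, landmark or time-varying exposure. The only timing statement in the item is that TB is assessed 15 to 16 months after enrolment, which is an assessment time. The protocol does not settle the clock:

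- Outcome Measures defines the 16-month outcome as "Number diagnosed with TB during 16-month follow-up", with no start.
- Post-3HP treatment describes TB screening for "up to 28 months after enrollment". The same paragraph defines loss to follow-up over a 12-month window after treatment.
- The risk-set footnote counts loss to follow-up from 10 to 28 months after 3HP ends, and closes follow-up after a 28-month post-treatment period.

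TB is looked for during treatment. At DOT and refill visits the pharmacy technician screens for symptoms and refers symptomatic participants: "The clinician will make all decisions regarding TB testing, initiation of TB treatment, and continuation/discontinuation of 3HP".

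**The concern.** The exposure is defined by what happens after follow-up may already have begun. With weekly dosing, dose 11 falls no earlier than 10 weeks after dose 1, and the window runs to 16 weeks. Suppose the clock starts at enrolment or initiation. A participant on course to complete, who is diagnosed with TB in week 7 and whose clinician stops 3HP, is then counted as an event among those with 10 doses or fewer. No completer can have an event of that kind. The completer group therefore has events removed and the other group has them added, whatever the drug does.

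A hazard ratio below 1 is what readers expect from completing 3HP, so the artefact would be easy to take for protection. Two analysts could also choose different clocks, get different ratios from the same data, and both claim to follow the SAP.

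**Working it through.** The plan gives no TB rate, event count or hazard ratio for this comparison, so there is no figure to reproduce. The check is an illustration under no true effect.

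**From the documents:** 552 per arm (SAP 2.5); 16 months, the only TB horizon among the SAP objectives (2.1); 28 months as the further protocol horizon; weekly doses and a 16-week window.

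**Assumed:** a share p = 0.80 would complete if TB did not intervene; TB rate L = 0.01 per person-year, constant; dose 11 at week w = 10; a share f of would-be completers with TB before dose 11 has 3HP stopped.

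**Formulas**

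- Risk over follow-up: R = 1 - exp(-L x 16/12) = 0.01324. Events per arm: 552 x 0.01324 = 7.31.
- Risk before dose 11: E = 1 - exp(-L x 10/52.18) = 0.001915. Share of all TB: s = E/R = 0.145.
- Events changing group: 552 x p x f x E = 0.21, 0.42 and 0.85 for f = 0.25, 0.5 and 1.
- Ratio, completers to others (the person-time shift is negligible): (1 - fs) / (1 + fs x p/(1 - p)).

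For f = 1: (1 - 0.145) / (1 + 0.145 x 4) = 0.54. With f = 0 the ratio is 1.00 throughout.

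| Setting | f = 0.25 | f = 0.5 | f = 1 |
|---|---|---|---|
| Base case | 0.84 | 0.72 | 0.54 |
| 28 months | 0.90 | 0.82 | 0.69 |
| Dose 11 at week 15 | 0.78 | 0.62 | 0.42 |
| 85% would complete | 0.80 | 0.66 | 0.47 |
| TB found only up to week 6 (SAT) | 0.90 | 0.82 | 0.68 |
| Half of diagnoses at the end assessment | 0.92 | 0.84 | 0.72 |

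The SAT row reflects the visit schedule: "At weeks 6 and 12, participants will return to the Mulago ISS clinic", so only one scheduled clinic visit falls between doses 1 and 11. With dose 11 at week 15 and f = 1, 1.27 events change group, the largest number in the table's 16-month settings.

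**Precision.** With SE of the log ratio = sqrt(1/a + 1/b), base-case events are 5.64 vs 1.67 at f = 0.25 (95% CI 0.15 to 4.7) and 5.00 vs 2.31 at f = 1 (0.11 to 2.6).

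**An effect in the other direction.** Screening happens at DOT and refill visits, so early stoppers are screened less. If a quarter or half of their TB in weeks 0 to 16 is never found, the 0.84 becomes 0.89 or 0.94, and the unbiased 1.00 becomes 1.06 or 1.13.

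**With a 16-week landmark.** Under equal detection the ratio is 1.00. Events before week 16 number 552 x (1 - exp(-0.01 x 16/52.18)) = 1.69, or 23% of 7.31, leaving 5.62. If a share m of early stoppers' TB from before week 16 is found only afterwards, the ratio is 1 / (1 + m x 1.69/5.62): 0.93 for m = 0.25 and 0.87 for m = 0.5.

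**The case against.** The strongest reply is that this hardly matters. Fewer than one event per arm changes group in the base case, and the intervals are too wide for anyone to claim protection. Simulated at those settings, a 5% log-rank test rejects roughly 6%, 9% and 16% of the time for a quarter, half and all stopping. Confounding by adherence would bar a causal reading even with a perfect clock. All of this stands and makes the point minor. It does not excuse leaving the clock undefined.

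The size also rests on inputs that the documents lack: the TB rate, how much TB appears before dose 11, and how often it stops 3HP. Excluding suspected active TB at entry could lower early TB below the constant-hazard figure. This stands too, so the ratios are illustrations.

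Four stronger readings are tempting and unsupported:

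- *The planned analysis is biased.* The post-treatment wording in the protocol allows a clock that starts after treatment among TB-free participants, and that clock avoids this bias.
- *TB during treatment ends 3HP.* The protocol leaves continuation to the clinician and says nothing on how often it would stop.
- *0.54 is the worst case.* It holds only for 80% completion with dose 11 at week 10; the table shows lower values.
- *Universal sputum testing at 16 months dilutes the bias.* Testing "regardless of any symptoms of TB" is specified at 28 months only. Table 2, footnote e ("Only if symptomatic, except at end of follow-up") belongs to a schedule running to month 28. At 16 months there is only the SAP's own assessment sentence.

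**Conclusion.** The omission is real: neither document fixes the time origin for this comparison, and the SAP sentence on the Cox model names the wrong groups. The direction is also clear, given both conditions: a clock from enrolment or initiation, and some TB before dose 11 leading to 3HP being stopped. Completion then looks protective under no effect. Without either condition, this bias is absent.

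The size is uncertain. Under the stated assumptions the null ratio is 0.84 to 0.54 over 16 months and 0.90 to 0.69 over 28 months. It is lower with later dose 11 or higher completion, and closer to 1 if many cases are found only at the end assessment. No more than about 1.3 of some 7 events per arm change group in the 16-month settings tabulated, and reduced screening of early stoppers can pull the other way. This is a minor point about a secondary, non-randomised analysis. The primary outcome and the randomised between-arm TB comparison are not touched.

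**What to change.** In SAP 3.7, item 2, second bullet:

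1. State the time origin.
2. Start this one analysis at a landmark 16 weeks after treatment initiation, among participants alive, TB-free and in follow-up. The protocol already recalls non-completers "at 16 weeks post-treatment initiation (for participants not completing treatment"), so no new visit is needed. Decliners have no initiation date: use 16 weeks after enrolment, or report them separately.
3. Compare at least 11 doses within 16 weeks with all others, and name these groups instead of the arms. As written, someone who takes 11 or more doses but finishes after week 16 falls in neither group.
4. Report TB before the landmark separately.
5. Label the result non-randomised, since confounding by adherence remains.

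The cost is SAP wording and a few lines of code. Under the base-case assumptions about 23% of events leave this analysis; they stay in the between-arm comparison. The landmark is not a complete cure: TB missed in early stoppers and found after week 16 still pushes the ratio below 1 under no effect (about 0.93 if a quarter carries over, 0.87 if half does). The SAP should state that as a limitation.
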